### 5.3 Study Duration:

This is a 2-year study. Eligible participants will be enrolled throughout the duration of the study. It is anticipated that study enrollment goal will be met six months prior to study ending in year 2. Individual participant's participation will approximately be three months from time of enrollment into the study. We anticipate the completion of all study procedures, including data analysis and results to report, will take approximately a year once the study has completed all data collection from study participants.

### 5.4 Use of radiation: N/A

### 5.5 Use of Center for Magnetic Resonance Research:

All participants who consent to MRI testing will get a 3T structural and functional MRI scan at baseline and after completion of the 3-month treatment course. The scanning protocol will be standardized between the two testing sites. We will collect i) brain structure (Multi Echo Magnetization Prepared Rapid Acquisition Gradient Echo, MEMPRAGE) ii) brain white matter integrity (Diffusion Weighted Imaging, DWI), iii) brain resting state functional connectivity (resting state functional Magnetic Resonance Imaging, rsfMRI), and iv) evoked responses to Motor Imagery (MI). MI involves asking individuals to envision themselves executing motor actions, without actual execution, a task that activates the same or similar neural systems as the actual execution of motor actions.

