## 5.0 Procedures Involved

### 5.1 Study Design:

This is a multi-center randomized, double-blinded placebo-controlled pilot clinical trial. Each site (Swedish Medical Center/Craig Hospital, UMN) will enroll and study 20 adults, 18 years of age and older with SCI. [name] will serve as PI, and [name] will serve as Co-I at UMN (local site). MRI data analysis will be conducted by [name] (Harvard University). [name] will receive a deidentified dataset and will have no human subject interactions. Research activities at the Swedish Medical Center/Craig Hospital will be conducted under a separate IRB protocol at Craig Hospital.

Participants who meet the eligibility criteria will be randomly assigned to active drug (escalating brivaracetam dose to 100 mg twice daily for 3 months) or placebo based on a randomization schedule developed by our biostatistician. This is a simple computer generated 1:1 scheme that randomly assigns participants to arm A or arm B. Study participants, research coordinators, and study personnel involved in outcomes assessments and analyses will all be blinded. The drug will be provided by RxArtisans pharmacy in Wayzata, MN. The active and placebo capsules will have identical appearance and consistency. Treatment assignment will be known only to the investigational drug pharmacies (RxArtisans). We have registered this pilot study with National Institutes of Health (NIH) clinical trials registry, [www.clinicaltrials.gov](http://www.clinicaltrials.gov) (NCT04379011). The pilot data generated by this effort will be used to power a subsequent multi-center clinical trial.

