### *15.1 Data Analysis Plan:*

For aim 1, the main outcome variables of interest include various dimensions of pain, mood (PHQ-9), life satisfaction (SWLS), resting state brain connectivity, and community integration (CHART-SF) measured at baseline and again at 3-months of treatment. Of particular interest is whether there is a difference in pain reduction from baseline to end of study between the treatment and control groups; this will be analyzed in this pilot with linear regression including terms for group and time and the interaction of group by time. We note that many of these instruments have bounded scores and we will include analyses that recognize these (via, e.g., non- linearities or recognize the bounds such as Tobit regression) Further exploratory analyses will examine the relationships (correlations) between changes in pain and changes in mood, life satisfaction, resting state brain connectivity, and community integration using linear regression.

For aim 2, we will use the same analytic approach we have refined in our 2 active rsfMRI studies. MRI data will be analyzed using the SPM12 based Conn toolbox 3 (Version 17f, Matlab R2018b). Preprocessing steps include realignment and unwarping, slice-timing correction, ART based identification of outlier scans for scrubbing, segmentation and normalization to MNI space, and 8 mm smoothing. Denoising steps include scrubbing, aCompCor, ICA-based denoising, Global Regression, and 0.008 to 0.09 Hz band-pass filtering). Three main comparisons will be evaluated: The effect of drug treatment on rsfMRI measures, the effect of pain intensity on rsfMRI measures (each via linear regression as in Aim 1), and the differences in rsfMRI measures between active drug responders and non-responders; this last will also be analyzed via linear regression; note, however, that this will be limited to those in the active group and people in the placebo group will not be included. First, we will evaluate region-of-interest (ROI) based functional connectivity in a set of anatomically defined regions known to be impacted in SCI and neuropathic pain: the periaqueductal gray, the bilateral thalamus, the amygdala, the hippocampus, the insula, anterior cingulate, the precentral and the post-central gyrus. Second, we will evaluate, on a voxel-by-voxel basis, amplitude of low frequency fluctuations (ALFF) and intrinsic resting state functional connectivity.

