## **23.0 Multi-Site Research**

**23.1** Study-Wide Number of Participants:

20 enrolled participants. 30 screened participants.

**23.2** Study-Wide Recruitment Methods:

We anticipate screening 30 individuals with SCI to recruit and enroll 20 participants across the 2 enrollment sites (Swedish Medical Center/Craig Hospital and University of Minnesota). The PI (Swedish Medical Center/Craig Hospital site) sees over 50 patients a year with severe sublesional neuropathic pain. Therefore, at Swedish Medical Center/Craig Hospital we will recruit potential participants from his clinical practice. The Department of Rehabilitation Medicine houses an ACGME-accredited, 12-month SCI Medicine Fellowship program. This fellowship leverages collaborative relationships with all specialty hospitals in the greater Minneapolis area providing acute inpatient rehabilitation for spinal cord injury, including Fairview Acute Inpatient Center, Minneapolis VA Medical Center, Regions Hospital, and Courage Kenny Rehabilitation Institute. Therefore, we will recruit participants at the University of Minnesota from each of our SCI Medicine Fellowship clinical sites. We will also utilize local patient representative organizations by sharing posters and sample text for social media recruitment. The Rocky Mountain Regional Spinal Injury System at Craig Hospital provides comprehensive inpatient rehabilitation to over 200 newly injured individuals with SCI every year and continues to treat nearly 1,100 individuals with SCI annually in outpatient programs,

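### No Aim 1 or Aim 2 regression has a site or scanner term: the drug-effect estimate survives a stable site offset, but its standard error is overstated and the between-person imaging comparisons can be confounded

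*Combined protocol and SAP*

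**What the plan says.** - **Sites and scanning.** Section 5.1: "Each site (Swedish Medical Center/Craig Hospital, UMN) will enroll and study 20 adults, 18 years of age and older with SCI". Section 5.5 covers acquisition: "The scanning protocol will be standardized between the two testing sites".
- **Allocation.** Section 5.1: "This is a simple computer generated 1:1 scheme that randomly assigns participants to arm A or arm B". No site stratum is mentioned.
- **Drug-effect model.** Section 15.1 uses "linear regression including terms for group and time and the interaction of group by time". The Aim 2 drug and pain-intensity models follow it: "each via linear regression as in Aim 1".
- **Responder comparison.** The third Aim 2 analysis is "the differences in rsfMRI measures between active drug responders and non-responders", and "this will be limited to those in the active group and people in the placebo group will not be included".
- **Standard errors.** Section 15.2 specifies heteroskedasticity-robust standard errors and names effect sizes and standard errors among the things the pilot should deliver for planning.
- **What is absent.** Sections 15.1 to 15.3 contain no site or scanner covariate, site random effect, harmonisation step or participant term.
- **Total sample.** Section 5.1 implies 2 x 20 = 40. Section 23.1 says "20 enrolled participants. 30 screened participants", and Section 23.2 spreads those 20 over both sites.

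**The concern.** A shared acquisition protocol does not guarantee that two scanners return the same signal level. ALFF, which Section 2.2 defines as the total power of the signal in a frequency band, is a level measure. Pain scores may also differ by site: under Section 23.2 one site recruits from the site investigator's own practice, the other from fellowship hospitals and patient organisations. Robust standard errors allow for unequal variances but do not remove a difference in level.

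Two results are at stake. One is the standard error that the follow-up trial would inherit. The other is the responder comparison, which serves the biomarker goal in Section 1.1. It compares people with each other, so nothing in the design balances site between the two groups.

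**Working it through.** The plan states no figure to reproduce: Section 15.2 gives no effect size, SD or power.

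**Inputs.** From the documents: two sites, 1:1 allocation, the three-term model, and N = 20 or 40. Assumed: sites and arms of equal size, within-site SD of 1, within-person correlation 0.6, site offset d (in SDs), true effect 0.8 SD, two-sided 5% level.

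**1. Drug-effect estimate.** With complete pairs, the group-by-time coefficient is (mean change, active) minus (mean change, placebo). A participant at the offset site has d added at both visits, so the change is (y1 + d) - (y0 + d) = y1 - y0. In simulation the coefficients with and without a site main effect agreed to about 1e-14 in every run.

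**2. Its reported standard error.** The model treats the two visits as independent rows, so the offset stays in the residual. With a 50:50 site split the residual variance is 1 + d²/4, and with n = N/2 per arm the SE is √[4(1 + d²/4)/n].

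| N | d = 0 | d = 1 | d = 1.5 |
|---|---|---|---|
| 20 | √(4/10) = 0.63 | √(5/10) = 0.71 | √(6.25/10) = 0.79 |
| 40 | √(4/20) = 0.45 | √(5/20) = 0.50 | √(6.25/20) = 0.56 |

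Simulation with robust standard errors at d = 1 gave 0.70 without site and 0.62 with it at N = 20, and 0.50 and 0.44 at N = 40. That is an overstatement of 12-13%; at d = 1.5 it is 26-27%. Carried into a sample-size formula, 1.12² = 1.25 and 1.13² = 1.28, so the follow-up would be 25-28% larger than needed on this account alone. Power for 0.8 SD is about 8% without site and 14% with it at N = 20, and 27% and 40% at N = 40.

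**3. The larger source of the excess.** The true spread of the estimate is √[2(1 - 0.6) x 2/n] = √0.16 = 0.40 at N = 20 and √0.08 = 0.28 at N = 40. Even with a site term the three-term model reports 0.62 and 0.44, because it ignores the pairing. A change-score analysis reports 0.39 and 0.28, with power about 47% and 79%. Adding site to it leaves power at 46% and 78%.

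**4. Site differences in change.** If change itself differs by site, a site main effect in the three-term model again leaves the group-by-time estimate unchanged. Site in a change-score model, or site-by-time, does adjust for it. With a 1 SD site difference in change, omitting site raised the variance of the change contrast by 22-26%.

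**5. Responders against non-responders.** Take equal sites, with response rates of 30% at site A and 60% at site B (assumed).
- Site B's share of responders: 0.60/(0.30 + 0.60) = 0.667.
- Site B's share of non-responders: 0.40/(0.70 + 0.40) = 0.364.
- Spurious difference: 0.303 x d, so about 0.3 SD at d = 1. At 40% and 60% it is (0.60 - 0.40) x 1 = 0.20 SD.

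This does not shrink as N grows. It applies to a level at one visit, such as the baseline activity named in Section 1.1; a stable offset would cancel if scan-to-scan change were compared. Section 15.1 does not say which is meant. The pain-intensity analysis carries the same risk wherever it compares people.

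**6. Cost of the term when sites are identical.** For change scores, (0.403/0.391)² = 1.06 at N = 20 and (0.287/0.283)² = 1.03 at N = 40. In the responder comparison the variance inflation is 1/(1 - r²), where r is the sample correlation of site with response. At the 30%/60% rates it averages about 1.20 with 20 scanned active participants and about 1.35 with 6. If response is unrelated to site it averages about 1.17 to 1.27 with 6 to 10.

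**The case against.** The strongest reply is that the drug-effect question concerns change from baseline and the model estimates it by group-by-time, so a stable scanner offset drops out whether or not a participant term is fitted. That is correct. A reader might infer from unstratified allocation that a chance difference in site mix becomes part of the estimated drug effect, or that omitting site inflates that estimate's variance by 17-53%. Neither holds for the planned contrast with complete pairs: the 17-53% range describes an arm comparison at a single visit, which Section 15.1 does not use for the drug effect. Leakage would need missing second scans, a change of scanner, drift, or a site difference in change, together with imbalance. Type I error was not inflated in any scenario run with the planned model (0.1-0.7%).

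It is also fair to say that the missing participant term costs more precision than the missing site term, that the documents give no site difference, so 1 and 1.5 SD are assumptions, and that this is a pilot with partly exploratory analyses.

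What the reply leaves standing is the overstated standard error, which is a stated product of the pilot, and the non-randomised Aim 2 comparisons, where cancellation and randomisation give no protection.

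**Conclusion.** The omission is real and cheap to repair; its importance is moderate. For the drug effect, an offset of 1 SD overstates the reported standard error by 12-13% and one of 1.5 SD by 26-27%, while the estimate is unaffected if each participant is scanned twice on the same scanner. For responders against non-responders, a 1 SD offset with response rates of 30% and 60% gives about 0.3 SD of spurious difference. These sizes rest on assumed offsets, response rates, equal sites and a within-person correlation of 0.6.

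Site imbalance should not be presented as a bias in the drug effect. How often it occurs also depends on unstated details: arms differ in site mix by 30 points or more in 27% of coin-flip allocations at N = 20 (8% at N = 40), but in 18% and 11% if arm sizes are fixed equal. Section 5.1 does not say which scheme is used, and the total N is itself contradictory.

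**What to change.** 1. Name site (scanner, for imaging) as a covariate in the Aim 1 and Aim 2 regressions and in the second-level imaging model.
2. For the drug effect, fit site in a change-score model, or site and site-by-time with a participant effect. A site main effect added to the three-term model would correct part of the standard error but could not address site differences in change.
3. State whether the responder comparison uses baseline level or change, and report it with and without the site term.
4. Report whether both scans of each participant came from the same scanner, and show the main results by site.
5. Reconcile the total N between Sections 5.1 and 23.1, since it determines how many terms the models can carry.

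The cost is one or two model terms. If the sites are identical, variance rises by about 3-6% in the full-sample models and by about 20-35% in the responder comparison with 6 to 20 scanned active participants. Scanning is optional and virtual participants are not scanned (Section 5.2), so the lower end of that range of numbers is plausible. The revision history records enrolment as complete, so stratified allocation is no longer available and the repair has to be made in the analysis.

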## 6.0 Data and Specimen Banking

### 6.1 Storage and Access:

## MEDICAL PROTOCOL (HRP-590)

PROTOCOL TITLE: Brivaracetam to Reduce Neuropathic Pain in Chronic SCI: A Pilot Clinical Trial  
VERSION DATE: 03/18/2024

All data used for this project will be obtained after receiving informed consent from all participants. The research material collected in this project are in the form of: (1) magnetic resonance imaging (MRI) records, (2) standardized patient-rated questionnaires, clinical assessments, and (3) blood serum.

Clinical data will be stored on Research Electronic Data Capture (REDCap), physical paper files will be kept in a locked file drawer in the study coordinator's office, and on encrypted servers (Box). Participant confidentiality will be safeguarded by the use of password protected databases and locked file cabinets. Research records will be stripped of all identifying information, with keys identifying individual participants available only to the PI or selected designees. Further, access to identifiable private information from study participants will only be accessible to study-related personnel who have met the training requirements for the responsible conduct of research, Good Clinical Practice, HIPAA, and data security, and who have completed all initial and annual study specific training.

Blood samples will be collected in the Fairview Clinical Research Unit (CRU), and stored locally in a -80 freezer at UMN. Blood samples will be labeled by ID number, type (plasma or serum), and date of draw. A password-protected tracking sheet will be used to link participants' blood samples with identifiable information (i.e., date of birth). This sheet will only be accessed by the IRB-approved study staff.

At the baseline and final evaluation, we will draw 38 ml of blood (20 mL plasma, 18 mL serum) after an overnight fast and store it at -80° Celsius until batch processing in the lab of the PI.

### 6.2 Data:

All clinical assessments, quantitative proprioceptive recordings, standardized patient-rated questionnaires will be stored on Research Electronic Data Capture (REDCap) and on encrypted servers. Imaging of brain activation (fMRI), and brain networks via functional resting-state (functional connectivity), and task-based (effective connectivity) will be preprocessed using the HCP preprocessing pipeline. MRI data will be stored in digital form on encrypted servers.

We will bank blood serum and plasma for long term storage. To minimize the risk of loss of privacy all records will be kept confidential and identified by study code only in the working databases. Blood samples will be stored without identifiers using only the study code.

## MEDICAL PROTOCOL (HRP-590)

PROTOCOL TITLE: Brivaracetam to Reduce Neuropathic Pain in Chronic SCI: A Pilot Clinical Trial  
VERSION DATE: 03/18/2024

### 6.3 Release/Sharing:

The results will be submitted for publication in scientific journals and presented at conferences. In case the scientific journals request the original database, then the de-identified xls file with scoring and codes will be shared on their protected databases.

## 7.0 Sharing of Results with Participants

### 7.1 Sharing Results:

No information will be provided to the participant unless the information indicates that the participant may be at risk for a serious illness known at the time of testing to be treatable. In that case, the study doctor will attempt to notify the participant. The research participant and their clinical care person(s) are responsible for further evaluation/follow-up in response to MRI incidental findings. Participants will be given the option to opt out of receiving any incidental findings.

### 7.2 Sharing Genetic Results: N/A

7.2.1 Disclosure of Results: N/A

7.2.2 Returning Results to Participants: N/A

Aggregate or individual results: N/A

Laboratory results: N/A

Plan for return of results to participants: N/A

Types of results to be returned to participants: N/A

7.2.3 Future analysis of genotypes: N/A

## 8.0 Study Population

### 8.1 Inclusion Criteria:

- 18 years of age or older
- Completed inpatient rehabilitation and living in the community
- Ongoing severe below-level neuropathic pain (daily average 9/10 or 10/10)
- Tried and failed to achieve adequate pain relief with the use of other drugs (previous pain management drugs failed to decrease their pain below a self-reported level of 9 out of 10)

## MEDICAL PROTOCOL (HRP-590)

### PROTOCOL TITLE: Brivaracetam to Reduce Neuropathic Pain in Chronic SCI: A Pilot Clinical Trial

VERSION DATE: 03/18/2024

- For people of child-bearing potential: currently practicing an effective form of two types of birth control (defined as those, alone or in combination, that result in a low failure rate (i.e., less than 1% per year) when used consistently and correctly).

#### 8.2 Exclusion Criteria:

- Progressive myelopathy secondary to posttraumatic cord tethering or syringomyelia
- Active use of drugs known to interact with brivaracetam: rifampin, carbamazepine, sodium oxybate, buprenorphine, propoxyphene, levetiracetam, and phenytoin.
- Brain injury or cognitive impairment limiting the ability to follow directions or provide informed consent
- Pregnancy or lactation
- Epilepsy or active treatment for seizure disorder
- Past or current suicidality
- Active treatment for psychiatric disease
- Drug addiction
- Moderate or heavy alcohol intake (up to four alcoholic drinks for men and three for women in any single day, and a maximum of 14 drinks for men and 7 drinks for women per week)
- Hepatic cirrhosis, Child-Pugh grades A, B, and C
- Impaired renal function
- Contraindications to brivaracetam or pyrrolidine derivatives including allergy
- Active clinically significant disease (e.g., renal, hepatic, neurological, cardiovascular, pulmonary, endocrine, psychiatric, hematologic, urologic, or other acute or chronic illness) that, in the opinion of the investigator, would make the patient an unsuitable candidate for this trial.
- History of malabsorption or other gastrointestinal (GI) disease that may significantly alter the absorption of brivaracetam
- Use of any investigational drug 30 days prior to enrollment in this study

People with contraindications to MRI including retained bullet fragments, noncompatible metal implants, and implanted devices such as non-MRI compatible baclofen pumps may still be eligible for the study; they will not participate in the MRI scans.

## MEDICAL PROTOCOL (HRP-590)

PROTOCOL TITLE: Brivaracetam to Reduce Neuropathic Pain in Chronic SCI: A Pilot Clinical Trial  
VERSION DATE: 03/18/2024

### 8.3 Screening:

A prescreening checklist will be administered to confirm basic eligibility prior to consenting. This includes confirming age, pain level, medication use, implanted medical devices or retained metal fragments, and other medical conditions. If participant meets basic eligibility requirements, we will request that they obtain medical clearance for study participation from their primary care provider or other medical professional, including collecting 3-4 tablespoons of blood for screening blood work and completing a physical exam and health history. The participant's insurance will be charged and they will be responsible for any associated copays or costs.

The participant's provider will provide UMN research staff with results via fax or email, or the participant may carry a hard copy. If the participant is a patient of Fairview, their medical records will be accessed directly by research staff who have obtained approval via the non-Fairview employed research staff (NERS) application process for conducting research tasks in Fairview facilities and systems.

